**c. Anticipated end date of study:**

This study is expected to be concluded in December 2025.

## 9. Locations of Study

VUMC/C-Saúde supports HIV care and treatment services in 149 clinical sites in the province. These sites range from small district-level hospitals to rural health posts. Our trial will involve four of these clinics (with a focus on urban facilities): 1) as a control site, 2) as a site implementing anti-stigma training, 3) as a site implementing resilience training, and 4) as a site implementing anti-stigma and resilience training.

Health facilities will be eligible for selection in the study if they serve at least 4,000 patients enrolled on ART who will be scheduled for clinic visit(s) during the study period. For study operational purposes, only HF in Quelimane City and Nicoadala districts will be considered for selection. **Table 5** below shows a list of health facilities meeting these criteria and from which study sites will be selected by study co-investigators in collaboration with DPS-Z/NIOZ study focal point. Site selection will also consider feasibility of study activities at the indicated HF.

**Table 5:** List of Health Facilities Eligible for Study Site Selection

HF Sites Eligible for Study Selection				
	District	Health facility	# of patients in Q1 (Oct – Dec 2022)	# of patients in Q2 (Jan – Mar 2023)
1	Nicoadala	CS Nicoadala	13113	12580
2	Quelimane	CS 17 de Setembro	7761	7637
3	Quelimane	CS Coalane	7074	6981
4	Nicoadala	CS Licuare	5882	6030
5	Quelimane	CS 24 de Julho	5921	5917
6	Quelimane	CS Chabeco	4698	4727
7	Quelimane	CS Namuinho	4741	4422
8	Quelimane	CS 4 de Dezembro	4180	4149

## 10. Data Management and Analysis

### Data Management and Security

**Survey data:** Data from the surveys, including sociodemographic data, will be entered into a secure, password-protected REDCap database by field staff trained in data entry using password-protected tablet devices. Data are kept in the VUMC-REDCap server. In the event that paper surveys are necessary to use (e.g., connectivity to REDCap database is temporarily unavailable), data will be initially captured on the paper survey and later entered into a REDCap database by field staff trained in data entry. In these cases, the original paper surveys will be locked in a file

cabinet in the C-Saude office in Quelimane for 5 years, after which time they will be destroyed once authorization by the PI ([name]) is received.

*In-depth interview data:* The in-depth interview data will be recorded; research staff will transcribe the data ideally within a month of the interview into a password protected Word document. After transcription and translation, the original recording will be deleted. Only the study team working on the analysis will have access to the interview data. The data files will be password-protected to ensure confidentiality.

Data from interviews will be transcribed (and if necessary translated from local language into Portuguese) at C-Saúde Quelimane office. Transcription data will be typed up into Word documents, and subsequently translated into English. We will randomly select 10% of the original interviews to be re-translated (back to Portuguese) to check for accuracy after translation. The English transcriptions will be imported into MAXQDA 2022® software or similar to be coded by [name] and a study assistant. The data will be password-protected to ensure confidentiality and will be stored in REDCAP to ensure security and backup of data.

The original audio recordings of the interviews, which will not include participant names or other identifiable information, will be locked in a file cabinet in the C-Saude office in Quelimane until they have been entered into the database and the data has been checked for errors. After this point they will be erased to ensure voices cannot be linked back to the transcripts. All paper copies of transcripts will be destroyed once they have been typed up, verified, and the electronic versions have been sent to VUMC. All electronic copies of transcripts will be kept in a password-protected folder on a secure server at VUMC for a period of 5 years, after which time they will be destroyed after authorization of the PI ([name]) to do so.

*Routine clinical data:* C-Saúde and other PEPFAR partner organizations within the province implement electronic patient tracking system (EPTS) databases using OpenMRS, to collect patient information on their HIV care, facilitating the maintenance of these records for the MOH's program. Data are extracted from patient clinical records into electronic patient tracking systems already established and functioning as part of routine monitoring by C-Saúde data entry specialists.

The OpenMRS databases are password protected and can only be accessed by C-Saúde monitoring and evaluation staff. The staff have specific training on data confidentiality; all C-Saúde staff sign confidentiality agreements prior to having any contact with patient clinical files. All data are reviewed by C-Saúde data supervisors at the district level and by data analysis officers based in the C-Saúde provincial office in Quelimane. Corrective measures are taken as necessary as a result of data quality audits and regular reviews of data. For this project, de-identified data will be extracted into a restricted dataset by C-Saúde employees from the existing OpenMRS databases and sent to a VUMC Biostatistician for analysis. All routine programmatic data are owned by the MOH. All routine programmatic data are part of the clinical record and as such will not be destroyed.

## **Data Analysis**

### **Objective 1:**

#### Quantitative Data Analysis

We will first conduct descriptive analyses. Our psychological and psychosocial measures are continuous or pseudo-continuous (e.g., sums of Likert-style questions) variables. Our outcomes

will be changes in psychosocial measures from baseline to follow-up. Descriptive analyses will include boxplots and summary measures by intervention arm (4 groups). Our formal analyses (those that test hypotheses) will take advantage of the factorial nature of this pilot cluster randomized control trial. These analyses will group together sites as receiving resilience intervention (yes vs. no) and receiving anti-stigma intervention (yes vs. no); therefore, results from two sites will be compared with results from two other sites. This gives us a larger sample size for each comparison and allows us to fit linear mixed effects models that include random effects to account for the correlation between measurements taken from participants at the same site while ensuring that the fixed effect of the intervention is identifiable. We will report results from models that are unadjusted and adjusted for a small number of HCW-level baseline covariates (age, sex, HCW role, and baseline measures of the outcome). Model diagnostics will be performed and outcome variables will be transformed, if necessary, to meet model assumptions.

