## 6. Design and Study Questions

We propose to conduct a pilot cluster randomized controlled trial to evaluate the effects of our interventions. Four health care facilities in Zambézia Province will be selected and then randomized to the control (standard-of-care [SOC]) or the intervention arms (anti-stigma training ONLY, resilience training ONLY, or anti-stigma + resilience trainings) (i.e., there will be one control arm and three intervention arms).

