**c. Calculations of Sample Size:**

**Objective 1:** Each of the four selected sites have no more than 25 health care workers providing HIV care, so we anticipate a maximum total of 100 health care workers equally divided between each intervention arm and the control arm. With  $n=25$  in all arms, assuming an intraclass correlation coefficient (ICC)=0.10, and two-sided type I error rate of 0.05, then we anticipate that we will have approximately 80% power to detect a difference of 1.07 standard deviations of the outcome (e.g., change in resilience score between baseline and after intervention), or the change in stigma score between baseline and after intervention) between the intervention vs. control for each of the two interventions. If ICC=0.05 (or 0.15), then we will have approximately 80% power to detect a difference of 0.85 (or 1.26) standard deviations.

For our qualitative interviews, we will continue to collect data until we have reached data saturation. Based on similar interviews conducted in 2022 (unpublished, IRB# 99/CIBS-Z/22), we believe we will reach saturation with no more than 40 interviews.

**Objective 2:** Each of the four health facility sites serve at least 4,000 patients enrolled on ART who will be scheduled for clinic visit(s) during the study period. With a minimum of  $n=4,000$  in each facility, assuming an ICC=0.05, and two-sided type I error rate of 0.05, then we anticipate that we will have approximately 80% power to detect a difference of 0.64 standard deviations of the outcome (e.g., proportion of time on medication) between the intervention vs. control. If ICC=0.025 (or 0.10), then we will have approximately 80% power to detect a difference of 0.45 (or 0.91) standard deviations.

The survey will be done in a sub-population of the cohort of HIV-positive patients at all four sites. Due to the exploratory nature, sample sizes for the patient surveys were not calculated based on existing assumptions. We estimate that 80 surveys per HF ( $n=320$ ) will provide us with the requisite baseline preliminary data on how they experience health care. For outcome

measures available on only these surveyed participants, we anticipate approximately 80% power to detect differences of 0.55, 0.71, and 0.96 standard deviations of the outcome assuming ICC of 0.025, 0.05, and 0.10, respectively.

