#### **Objective 2:**

With Objective 2 most of our outcomes are continuous measurements, and analyses will be similar to those described above: linear mixed effects models that take advantage of the factorial nature of outcome, with clusters defined as study sites, and unadjusted and adjusted for a small number of PLHIV-level covariates (age, sex, educational level, marital status, language, duration on ART, and history of ART medication pick-ups within the previous 6 months). For binary outcomes (e.g., undetectable viral load), we will fit generalized linear mixed effects models with a logit link function.

Every patient is given 30, 60, 90, or 180 days to pick up their ART medication, as indicated in the medical charts. If a patient picks up medication after the indicated/scheduled date, they will be considered "non-adherent" for each day after their specific pick-up date; this will be assessed over the course of the 6-month follow-up and will be treated as a continuous variable (a proportion between 0 and 1 for each participant). Participants who are lost to follow-up from the health facility during the 6-month follow-up period will be considered "non-adherent" for the days that they are lost. For persons who die or are known to have transferred care outside of the catchment area, the proportion of time on medication will be computed using only time prior to death or transfer of care. For our primary retention outcome (proportion of time on medication), normality assumptions are unlikely to hold, perhaps even after data transformation. Hence, we will fit a cumulative probability model (CPM) with fixed effects for the clinics. The CPM is well-suited for this setting because it does not require symmetry/normality in the outcome (which is bounded between 0 and 1 and likely not normal); in the absence of covariates, it reduces to the Wilcoxon rank sum test. The CPM has been shown to perform well in settings investigating medication adherence. Specifically, the distribution of the proportion of time on medication will be modeled as

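### The mixed-model tests on four sites name no site-level degrees of freedom; with a normal or person-level reference, their type I error would be about 11–21% for the staff co-primary outcomes

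*Combined protocol and SAP*

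**What the plan says.** Section 6 sets the design: "Four health care facilities in Zambézia Province will be selected and then randomized to the control" or to one of three intervention arms, so each arm is a single site. Section 10 (Objective 1, Quantitative Data Analysis) describes the formal, hypothesis-testing analyses as factorial: "results from two sites will be compared with results from two other sites". Clustering is handled by "linear mixed effects models that include random effects to account for the correlation between measurements taken from participants at the same site".

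Objective 2 carries this over to patients through "linear mixed effects models that take advantage of the factorial nature of outcome, with clusters defined as study sites", and for binary outcomes through "generalized linear mixed effects models with a logit link function". Proportion of time on medication is treated separately, with a cumulative probability model (CPM).

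For the mixed models the plan does not say whether REML or ML is used, whether one or both trainings enter each model, or which reference distribution, df or small-sample correction applies.

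Section 7c gives the staff power inputs: "Each of the four selected sites have no more than 25 health care workers providing HIV care", and "assuming an intraclass correlation coefficient (ICC)=0.10, and two-sided type I error rate of 0.05", leading to "approximately 80% power to detect a difference of 1.07 standard deviations of the outcome". The corresponding figures are 0.85 SD at ICC 0.05 and 1.26 SD at ICC 0.15. Sections 8a and 12 say that the pilot is not fully powered and that four sites are limiting. Neither mentions type I error or interval coverage.

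**The concern.** A random site effect accounts for clustering only as well as the between-site variance can be estimated. With four sites and site-level treatments, that variance rests on 2 df or 1 df. A normal or person-level reference treats it as if it were known. Often it is also estimated as exactly zero, and the standard error then ignores clustering altogether. Both make intervals too narrow. Since the plan names no reference, the analyst may simply take whatever the software supplies.

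At stake are the p-values and intervals for resilience, HIV stigma and the patient survey scores. Section 12 says that the trial should show which training works best and inform a fully powered trial, so false positives would carry forward into that design.

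**Working it through.** **Inputs.** Four sites, two versus two (sections 6 and 10). Staff: m = 25 per site, ICC 0.05/0.10/0.15. Patient survey: m = 80 per site, ICC 0.025/0.05/0.10. Two-sided 5% (all section 7c). Total variance is set to 1.

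**Step 1: reproduce the plan's power.** The variance of a site mean is V = ICC + (1 − ICC)/m. The difference between two two-site averages has variance V/2 + V/2 = V.
- At ICC 0.10, V = 0.10 + 0.90/25 = 0.136 and SE = √0.136 = 0.369.
- The plain normal formula gives (1.96 + 0.84) × 0.369 = 1.03 SD, not 1.07.
- Expressing the effect in units of the expected within-arm SD, with N = 4m, uses the factor [(N − 2) − 2(m − 1)ICC]/(N − 2) = (98 − 4.8)/98 = 0.951. The SE becomes 0.369/√0.951 = 0.378. A t-test with the ICC taken as known and 86 person-level df then gives 1.071 SD.
- The same calculation gives 0.850 and 1.265 SD at ICC 0.05 and 0.15 (stated 0.85 and 1.26; df about 95 and 74). For the survey it gives 0.545/0.708/0.963 (stated 0.55/0.71/0.96).

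The stated power therefore makes no allowance for estimating between-site variance from four sites.

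**Step 2: the df that exist.** Four site means, less the intercept and the training terms: 4 − 1 − 1 = 2, or 4 − 1 − 2 = 1. The 5% critical values are 4.30 and 12.7, against 1.96.

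**Step 3: type I error with a 1.96 cut-off.** 400,000 null trials per setting, normal outcomes, equal site sizes, no covariates. With balanced data, REML gives the training effect a variance of MSB/m, where MSB is the between-site residual mean square. If MSB does not exceed the within-site mean square, site variance is set to zero and the two are pooled.

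| Outcome | ICC | REML, one training | REML, both |
|---|---|---|---|
| Staff, m = 25 | 0.05 | 10.8% | 12.4% |
| | 0.10 | 14.1% | 17.5% |
| | 0.15 | 15.7% | 20.5% |
| Survey, m = 80 | 0.025 | 12.7% | 15.3% |
| | 0.05 | 15.6% | 20.3% |
| | 0.10 | 17.5% | 24.3% |

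Sensitivity (staff settings):
- ML is worse: 15.6/21.1/24.2% (one training) and 18.7/27.4/32.7% (both).
- A t reference on person-level df changes the REML rates by less than 1 point.
- A Satterthwaite-type df that reverts to person level when site variance is estimated as zero still gives about 7% (one) or 10–13% (both).
- Site variance is estimated as zero in 17–35% of trials (one) or 33–49% (both).
- Since 25 per site is a maximum: at 15 per site the rates are 8.8–13.9% (one) and 9.8–17.2% (both). Unequal sites of 25/22/18/15 give about 9–20%.
- At ICC 0 the rate is about 4%; at ICC 0.01, about 6%.
- A t-test on the four site means gives 5.0% for both staff and survey outcomes.

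**Step 4: what a valid reference costs in power.** For 80% power the noncentral t needs a difference of 5.653 SE at 2 df and 16.33 SE at 1 df. With √V = 0.2966/0.3688/0.4290 at ICC 0.05/0.10/0.15:
- 2 df: 1.68/2.08/2.43 SD.
- 1 df: 4.8/6.0/7.0 SD.

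At the effects stated in section 7c, power falls from about 80% to about 36–38% (2 df) or 18% (1 df).

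**The case against.** The strongest reply is that the plan never prescribes the faulty test. A mixed model does not imply a Wald z-test: Wald intervals are named only for the CPM. For the staff outcomes, the same REML model referred to t on between-site df rejects a true null in only 0.2–1.6% of trials (2 df) or almost never (1 df). That stands. A reader might infer that the protocol specifies an invalid test, or that any mixed model on four sites is invalid; the documents support neither. What remains is that the plan leaves open the choice that decides validity, that its own power calculation made the choice in the large-df direction, and that common defaults fail.

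A reader might also infer an error near 30% for chart-review outcomes. That needs 4,000 patients per site and both trainings in a linear mixed model. The one clearly continuous chart outcome the plan names, proportion of time on medication, goes to the CPM, and viral suppression and six-month retention are yes/no. The 30% figure has no clear target here.

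The rates are also conditional. The text fits one training per model as well as two, and one training gives the lower rates. If the other training truly shifts the outcome by 0.5 SD and is left out, the REML rate falls to 4–10%.

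Finally, this is a pilot with acknowledged limits. That excuses low power, but not intervals and p-values that are miscalibrated without notice.

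**Conclusion.** The concern holds as a missing specification with material consequences. Under REML with a normal or person-level reference, a nominal 5% test would reject a true null in about 11–16% of trials (one training) or 12–21% (both) for the staff co-primary outcomes, and about 13–17% or 15–24% for the patient survey outcomes. ML would be worse.

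These figures rest on the plan's own ICCs and cluster sizes, normal outcomes, no covariates and equal sites. They do not apply at ICC near zero, where there is no inflation. The logit mixed model for binary outcomes has the same four-site structure, but its error was not quantified. The CPM is outside this point.

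**What to change.** In section 10, for each mixed-model analysis:

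1. State the estimator and whether one or both trainings enter the model.
2. Base intervals and any p-values on site-level df. One method that holds 5% is a two-stage analysis: adjust for covariates at person level, then compare the four adjusted site means with a t reference on 2 df (one training) or 1 df (both). With one training, any real effect of the other training goes into the residual and widens the interval.
3. Alternatively, report mixed-model estimates and ICCs with no significance claims.
4. State the corresponding choice for the logit models.

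A site-level permutation test is no way out: a two-versus-two split has six allocations, so the smallest two-sided p-value is 2/6 = 1/3.

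Trial conduct does not change. The cost is some extra analysis and much wider intervals: detectable staff differences of about 1.7–2.4 SD at 2 df and 5–7 SD at 1 df. At 1 df, testing is of little practical use. The section 7c power figures should be restated on this basis and the results presented as pilot estimates.

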#### Qualitative Interview Analysis:

Within two weeks of each interview, the research assistant and the PI will meet to discuss the findings. Audio files will be transcribed by a research assistant. The PI and a research analyst will code and analyze the interviews using MAXQDA 2022 software or similar. Thematic analysis will be used to identify responses to our questions about the drivers, core facilitators, and barriers to intervention acceptability and success. Data will be coded by two independent coders to ensure that Cohen's Kappa is >85%. Three code maps will be developed to categorize data: (1) To understand the social, structural, and informational drivers, facilitators, and barriers to acceptability of resilience and anti-stigma training and (2) The potential of project sustainability, including interest, integration, and funding.

#### **Objective 2:**

With Objective 2 most of our outcomes are continuous measurements, and analyses will be similar to those described above: linear mixed effects models that take advantage of the factorial nature of outcome, with clusters defined as study sites, and unadjusted and adjusted for a small number of PLHIV-level covariates (age, sex, educational level, marital status, language, duration on ART, and history of ART medication pick-ups within the previous 6 months). For binary outcomes (e.g., undetectable viral load), we will fit generalized linear mixed effects models with a logit link function.

Every patient is given 30, 60, 90, or 180 days to pick up their ART medication, as indicated in the medical charts. If a patient picks up medication after the indicated/scheduled date, they will be considered "non-adherent" for each day after their specific pick-up date; this will be assessed over the course of the 6-month follow-up and will be treated as a continuous variable (a proportion between 0 and 1 for each participant). Participants who are lost to follow-up from the health facility during the 6-month follow-up period will be considered "non-adherent" for the days that they are lost. For persons who die or are known to have transferred care outside of the catchment area, the proportion of time on medication will be computed using only time prior to death or transfer of care. For our primary retention outcome (proportion of time on medication), normality assumptions are unlikely to hold, perhaps even after data transformation. Hence, we will fit a cumulative probability model (CPM) with fixed effects for the clinics. The CPM is well-suited for this setting because it does not require symmetry/normality in the outcome (which is bounded between 0 and 1 and likely not normal); in the absence of covariates, it reduces to the Wilcoxon rank sum test. The CPM has been shown to perform well in settings investigating medication adherence. Specifically, the distribution of the proportion of time on medication will be modeled as

$\text{logit}(P(Y \leq y)) = \beta_0(y) + \beta_1 \text{Intervention} + \beta_s \text{site} + \beta_x X$ , where  $\beta_1$  is the effect of the intervention on the log-odds ratio scale. Our primary objective is to test the null hypothesis,  $H_0: \beta_1 = 0$ . We will provide estimates of  $\beta_1$ , 95% Wald confidence intervals, and two-sided p-values. As with our other analyses, we will take advantage of the factorial nature of the model by grouping interventions as receiving resilience intervention (yes vs. no) and receiving anti-stigma intervention (yes vs. no). An interaction between the two interventions will also be assessed to see, for example, if the interventions are synergistic. The primary model will be adjusted for study site to acknowledge similarities between patients at the same site, and it will also be adjusted for a small number of patient-level baseline covariates, that are usually predictive of adherence to medications (e.g., age, sex, and education). In the model with the interaction between two interventions, study site will not be included so that the interaction effects are identifiable. In additional crude secondary analyses, we will investigate how changes in HCW measures correlate with patient outcomes by including average HCW metrics in models, replacing study site with this continuous variable. These latter analyses will be very much exploratory, as with only four study sites, we will have limited information to estimate these associations.

We will also compute three secondary measures of patient retention:

- (1) Monthly medication pick-up. Specifically, measured from the first day of ART initiation, any ART medication pick-up between days 16 and 45 will count as medication pick-up during month 1, any medication pick-up between days 46 and 75 will count as medication pick-up during month 2, and so forth, up until 6 months (i.e., medication pick-up between day 346 and 375); if the patient was enrolled on a three month pick up we will calculate on time pickups using the mark 15 days before and 15 days after the scheduled visit.
- (2) Monthly medication pick-up using a “re-setting” of the ART medication pick-up timeframe for each subsequent month. Specifically, calculating next scheduled ART medication pick-up from the date of last (most recent) ART pick-up (*data to be obtained from “master card” documentation*), any ART medication pick-up between days 16 and 45 from next scheduled date will count as medication pick-up for that specific month. With each date of last (most recent) ART pick-up, the window for next scheduled medication pick-up will adjust accordingly;
- (3a) For patients on monthly medication pick up. Retention at 6 months based on Mozambique Ministry of Health (MoH) guidelines. Specifically, at days 180 and 365 if the patient has had a documented ART pick-up within 59 days of their last scheduled pick-up date (*data to be obtained from pharmacy FILA form*), then they will be considered retained at that time point. If the patient has not had a documented ART pick-up in  $\geq 60$  days from their last scheduled pick-up date, they will be considered not retained (i.e., lost to follow-up);
- (3b) For patients on a differentiated care model. Retention at 6 months will look at the most recent ART medication pick-up that occurred during the first 180 days and the date of the next scheduled pick-up falling within the 180 days or beyond; if that day falls before day 121 after initiating ART, the patient would not be considered retained at 6 months.

